9.6. Analysis methods – secondary outcomes

A template for reporting all the secondary outcomes is given in Appendix D6.

Patient-reported QoL

For the RATE-AF trial, questionnaires SF-36v2, EQ-5D-5L and AFEQT are administered at baseline, 6 months and 12 months.

Up-titration visits:

These questionnaires are also administered for each patient at their last up-titration visit.

Note: the data for last up-titration visit is not done at any scheduled time-point due to the fact that each patient will have different up-titration visits (i.e. some will have 6 and some may only have 1) and so for this reason the data collected for last up-titration visit will only be summarised by treatment arm and no formal analysis for this data will be conducted.

- **SF-36v2 global and domain specific scores at 6 and 12 months**

The data for these outcomes are continuous in nature and the computation for the global and domain specific scores is described in the data manipulations section 9.4. The mean and standard deviation along with minimum and maximum values for global and domain specific scores will be presented by treatment arm and time-point.

The global and domain-specific scores will be analysed separately at 6 and 12 months using the same analysis methods as described in section 9.5. for primary outcome:

- Physical component summary (PCS) score at 12 months
- Mental component summary (MCS) score at 6 months and 12 months
- Physical Function score at 6 months and 12 months

- Role Limitation Due to Physical Problems score at 6 months and 12 months
- Role Limitation Due to Emotional Problems score at 6 months and 12 months
- Social Functioning score at 6 months and 12 months
- Mental Health score at 6 months and 12 months
- Energy/Vitality score at 6 months and 12 months
- Pain score at 6 months and 12 months
- General Health Perception score at 6 months and 12 months

The range for each domain of the SF-36v2 is from 0=worst score to 100=best score. The Bisoprolol arm will again be used as a reference category for all model based analysis for SF-36v2 and so higher values will indicate better outcome for Digoxin arm.

For SF36v2 PCS, additional secondary analysis will also be conducted using a mixed effects repeated measures model. The outcome in the model will be the repeated measure for PCS score and independent variables will be treatment arm, all minimisation variables, age at randomisation and baseline LVEF. Time (in days) will also be included in the model and a constant treatment effect over time will be assumed in the first instance, however a treatment by time interaction term will also be included in the model to check for its significance. If interaction is significant ($p < 0.05$), then estimates at each time point will be produced from the model including the interaction term. An unstructured covariance data structure will be used in the model. Results will be presented as adjusted mean difference and 95% confidence interval.

- **EQ-5D-5L summary index and visual analogue scale at 6 and 12 months**

The data for these outcomes are continuous in nature and the computation for the index summary score is described in the data manipulations section 9.4. The visual analogue score (VAS) is obtained from a scale so this score doesn't need to be derived. The mean and standard deviation along with minimum and maximum values for index summary score and VAS score will be presented by treatment arm and time-point.

The following will be analysed separately at 6 and 12 months using the same analysis methods as described in section 9.5. for primary outcome:

- EQ-5D-5L summary index score at 6 months and 12 months
- EQ-5D-5L visual analogue scale score at 6 months and 12 months

The range for summary index is from -0.285=worst score to 1=best score and for visual analogue score is from 0=worst score to 100=best score. The Bisoprolol arm will again be used as a reference category for all model based analysis of EQ-5D-5L and so higher values will indicate better outcome for Digoxin arm.

- **AFEQT overall score at 6 and 12 months**

The data for this outcome is continuous in nature and the computation for the AFEQT overall score is described in the data manipulations section 9.4. The mean and standard deviation along with minimum and maximum values for AFEQT overall score will be presented by treatment arm and time-point.

The following will be analysed separately at 6 and 12 months using the same analysis methods as described in section 9.5. for primary outcome:

- AFEQT overall score at 6 months and 12 months

The range for AFEQT overall score is from 0=complete disability to 100=no disability. The Bisoprolol arm will again be used as a reference category for the model based analysis of this and so higher values will indicate better outcome for Digoxin arm.

Cardiac function

- **Echocardiographic LVEF at 12 months**

The data for this outcome is a continuous score (presented as a percentage of volume ejected) and is also categorised using the following categories; "<40%", "40-49%", "≥50%". This data is collected at baseline and at

12 months. This data will be summarised as the mean, standard deviation, minimum and maximum values for the continuous score as well as number and percentage for the categories by treatment arm and time-point.

The main analysis of this data will be based on the continuous data so this outcome will be analysed using the same analysis methods as described in section 9.5 for primary outcome. For this outcome only, additional covariates for history of myocardial infarction (MI) at baseline, coronary angioplasty or stents (PCI) at baseline and coronary artery bypass surgery (CABG) at baseline will also be adjusted for in the model. Higher values of LVEF are considered better and since the Bisoprolol arm will again be used as a reference category for the model based analysis of this, higher values will indicate better outcome for Digoxin arm.

- **Diastolic function (E/e' and composite of diastolic indices) at 12 months**

The data for E/e' is a ratio and so continuous in nature. This data is collected at baseline and at 12 months. The mean and standard deviation along with minimum and maximum values will be presented by treatment arm and time-point.

This outcome will be analysed using the same analysis methods as described in section 9.5 for primary outcome. Lower values of E/e' are considered better and since the Bisoprolol arm will again be used as a reference category for the model based analysis of this, lower values will indicate better outcome for Digoxin arm.

The data for the composite of diastolic indices is a binary (yes/no) and will be computed as described in the data manipulations section 9.4. This data is collected at baseline and 12 months and will be summarised as number and percentage by treatment arm and time-point. The analysis for this outcome will be conducted using a logistic regression model, where the outcome will be the binary category (yes/no) at 12 months and independent variables in the model being the baseline category, treatment arm, all minimisation variables, age at randomisation and baseline LVEF. An adjusted odds ratio and 95% confidence interval will be estimated from the logistic regression model.

- **Change in heart rate**

The data type for heart rate is continuous in nature. This data is collected at baseline, 6 months and at 12 months. The mean and standard deviation along with minimum and maximum values will be presented by treatment arm and time-point for 1) Radial heart rate, 2) Apical heart rate, 3) 12-lead ECG heart rate, and 4) 24-hour ambulatory average heart rate. The 24-hour ambulatory heart rate is only measured once and so no baseline score will be there to adjust for it in analysis.

These outcomes will be analysed using the same analysis methods as described in section 9.5 for primary outcome and analysis will be done separately for 6 and 12 month time-points.

A scatter plot of radial vs apical heart rate at each time point will be produced to visualise the radial-apical discrepancy.

Functional assessment

- **Six-minute walking distance at 6 and 12 months**

The data for this outcome is continuous in nature and this test is conducted at baseline, 6 months and 12 months. The time (measured in min/s) and distance (measured in metres) are only recorded if the patient did the test. Therefore this data will be summarised by treatment arm and time-point with respect to the number of patients conducting the test, the mean and standard deviation, median and IQR as well as minimum and maximum values for time and distance covered. Reasons for stopping the test prematurely were also collected and so this will also be summarised by treatment arm and time-point.

The main endpoint for this outcome is the distance (in metres) walked and so this will be analysed using the same analysis methods as described in section 9.5 for primary outcome and analysis will be done separately for 6 and 12 month time-point.

- **Change in European Heart Rhythm Association (EHRA) class at 6 and 12 months**

The data for this outcome is categorical in nature and in 5 orderly categories; 1=None, 2a=Mild, 2b=Moderate, 3=Severe, 4=Disabling. This data is collected as baseline, 6 months and 12 months. This data will be summarised as number and percentage by treatment arm and time-point with respect to the EHRA class.

The analysis for this outcome will be conducted using an ordinal logistic regression model, where the outcome will be the EHRA class at follow up (with EHRA class 1 being the reference category) and independent variables in the model being the baseline EHRA class, treatment arm, gender, age at randomisation and baseline LVEF. An adjusted odds ratio and 95% confidence interval will be estimated from the ordinal logistic regression.

Higher EHRA class is considered to be a worse outcome and since the Bisoprolol arm will be used as a reference category in the model, higher values will indicate worse outcome for Digoxin arm.

Note: separate analysis will be done for 6 month and 12 month time-point.

We will also code this outcome as a binary “yes/no” variable where “yes” will be determined if patients had a 2 class improvement in the EHRA class from baseline. The full details for the computation of this are described in the data manipulations section 9.4.

The analysis for this outcome will be conducted using a logistic regression model, where the outcome will be the computed binary variable “yes/no” (with yes being the reference category) and independent variables in the model being treatment arm, gender, age at randomisation and baseline LVEF. An adjusted odds ratio and 95% confidence interval will be estimated from the logistic regression model.

Since we are modelling whether patients had an improvement from baseline and that the Bisoprolol arm will be used as a reference category in the model, higher values will indicate better outcome for Digoxin arm.

Note: again separate analysis will be done for 6 month and 12 month time-point.

Biomarkers

- **Change in NTpro-B-type natriuretic peptide (NTpro-BNP) levels**

The data for NTpro-BNP is continuous in nature and likely to be skewed and not normally distributed. Hence this data will need to be log-transformed first before analysis (see section 9.4 for more details). This data is collected at baseline, 6 month and 12 month. The raw untransformed data will be presented as mean standard deviation, median and interquartile range along with minimum and maximum values by treatment arm and time-point.

This outcome (log-transformed score) will be analysed using the same analysis methods as described in section 9.5 for primary outcome. Higher values of NTproBNP are considered worse and the Bisoprolol arm will again be used as a reference category for the model based analysis. Since we will be modelling the log-transformed scores and then exponentiate the effect size, the outcome will be in terms of geometric mean ratio and so values <1 will indicate better outcome for Digoxin arm.

Note: separate analysis will be done for 6 month and 12 month time-point.

Feasibility outcomes

- Recruitment target of 3 patients per week across all participating centres
- Compliance and reasons for non-compliance
- Number of withdrawals and losses to follow-up (with reasons)
- Drug discontinuation rate and adverse reactions requiring drug discontinuation
- Number of patients needing therapy-induced requirement for additional treatment
- Population-specific standard deviations (SD) and proportions:
 - SD of SF36 physical functioning score at 6 and 12 months
 - SD of SF36 overall score at 6 and 12 months

- SD of AFEQT overall score at 6 and 12 months
- SD of LVEF and E/e' scores at 6 and 12 months
- Unplanned hospitalisation admissions rates
- Cardiovascular Events (particularly mortality, thromboembolic events, myocardial infarction and cardiovascular interventions)

No formal model based analysis will be conducted for the feasibility outcomes and outcomes will be summarised using appropriate summary statistics.

A template for reporting this data is given in Appendix D7.

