9.1. Covariate adjustment

In the first instance, intervention effects between groups for all outcomes will be adjusted for the baseline score (where appropriate), minimisation parameters (Gender, baseline EHRA) as well as age at randomisation and

baseline LVEF (as continuous variables). The minimisation variable EHRA is a categorical score with the following categories (1, 2a, 2b, 3, 4) and for minimisation, this score was categorised into (class 1, 2a) and (class 2b, 3, 4). However for the analysis we will be adjusting this variable in its original 5 categorical form.

The Bisoprolol arm will be used as a reference category for all model based analyses.

For some binary outcomes, sometimes the effect size to be estimated of interest is the relative risk rather than the odds ratio and so for these outcomes, a log-binomial model is often used. However there are convergence issues with this type of model and so if the log-binomial model fails to converge, a Poisson regression model with robust standard errors will be used to estimate the same parameters.⁷ If this also fails to converge, unadjusted estimates will be produced from the log-binomial model. It will be made clear in the final report why this occurred (e.g. not possible due to low event rate/lack of model convergence).

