9.5. Analysis methods – primary outcome(s)

The primary outcome is the SF-36v2 physical component summary (PCS) score at 6 months.

The data for this outcome is continuous in nature and the computation for this score is described in the data manipulations section 9.4. The mean and standard deviation along with minimum and maximum values for the PCS score will be presented by treatment arm.

Data will be analysed using a linear regression model with outcome being the 6 months PCS score and independent variables in the model being the baseline PCS score, treatment arm, all minimisation variables, age at randomisation and baseline LVEF. An adjusted mean difference and 95% confidence interval will be estimated from the linear regression model and the p-value from the associated model will be produced. The Bisoprolol arm will be used as a reference category in the model and so higher values will indicate better outcome for Digoxin arm. A template for reporting the primary outcome is given in Appendix D5.

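### The additional repeated-measures model for PCS (SAP 9.6) lists no baseline PCS and names no outcome visits; as written it gives up precision that costs nothing to keep.

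*SAP*

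**What the plan says.** SAP 9.6 adds a mixed effects repeated-measures model for PCS. On outcome and covariates it says: "The outcome in the model will be the repeated measure for PCS score and independent variables will be treatment arm, all minimisation variables", followed by age at randomisation and baseline LVEF. On time: "Time (in days) will also be included in the model and a constant treatment effect over time will be assumed in the first instance". An arm-by-time interaction is tested, and if p<0.05, "then estimates at each time point will be produced from the model including the interaction term". The covariance is to be unstructured.

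The neighbouring text reads as follows.

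- SAP 9.5, the primary model for the same score at 6 months: "independent variables in the model being the baseline PCS score, treatment arm, all minimisation variables, age at randomisation and baseline LVEF".
- SAP 9.1, the general rule: "intervention effects between groups for all outcomes will be adjusted for the baseline score (where appropriate), minimisation parameters (Gender, baseline EHRA", plus age and baseline LVEF.
- SAP 9.6, the bullet heading above the model: "SF-36v2 global and domain specific scores at 6 and 12 months".
- SAP 9.6, the schedule: "questionnaires SF-36v2, EQ-5D-5L and AFEQT are administered at baseline, 6 months and 12 months".
- SAP 9.6, on the last up-titration visit: "the data collected for last up-titration visit will only be summarised by treatment arm and no formal analysis for this data will be conducted".
- Protocol 12.3.1 and 12.3.2: the primary ANCOVA adjusts for baseline score, and other continuous outcomes follow the same method.

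The PCS table in Appendix D6 covers only the 12-month linear regression. No template row or footnote there fixes the covariates or visits of the repeated-measures model.

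**The concern.** The covariate list in SAP 9.6 repeats every item of the SAP 9.1 rule except the baseline score. It gives no reason, whereas the same section does explain why 24-hour heart rate has no baseline to adjust for. The visits that make up the repeated measure are also left open. The up-titration visit is ruled out, so the only doubt is whether baseline is an outcome row. Two competent analysts could therefore fit different models.

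This is the only planned analysis that combines both follow-up visits for PCS. Followed literally, with outcomes at 6 and 12 months, it discards a prognostic value that is already collected. A baseline outcome row would raise a different problem: a constant arm effect, or one linear in days, would be imposed on a visit where randomisation makes the expected difference zero.

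**Working it through.** **The plan's own figure.** SAP 4.7 gives 144 evaluable patients for 0.5 SD, 85% power and two-sided alpha 0.05. Per arm, n = 2(1.960 + 1.036)²/0.5² = 71.8, so 72 per arm and 144 in all. Then 144/0.9 = 160. Both figures reproduce.

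**Inputs.** 72 per arm comes from SAP 4.7. The PCS correlations between visits and the variance explained by the listed covariates are not in the documents. I assume equal SDs, a common correlation r of 0.3 to 0.7, and a fraction e of variance explained by the other covariates at every visit (0, 10% or 20%). The unstructured covariance is taken as the residual covariance between visits. Effects are in SD units.

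**Outcomes at 6 and 12 months, constant effect.**

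- Without baseline PCS: variance = (2/72) × A, where A = (1 + r − 2e)/2.
- With baseline PCS: variance = (2/72) × [A − (r − e)²/(1 − e)].
- Power = Φ(effect/SE − 1.96).

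Example, r = 0.5 and e = 0. Without: √(0.75 × 2/72) = 0.144. With: √(0.50 × 2/72) = 0.118. The ratio is 1.22.

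| r | e | SE without | SE with | Ratio | Power for 0.3 SD, without / with |
|---|---|---|---|---|---|
| 0.3 | 0 | 0.134 | 0.125 | 1.08 | 61% / 67% |
| 0.5 | 0 | 0.144 | 0.118 | 1.22 | 55% / 72% |
| 0.7 | 0 | 0.154 | 0.100 | 1.54 | 50% / 85% |
| 0.3 | 10% | 0.124 | 0.119 | 1.04 | 68% / 72% |
| 0.5 | 10% | 0.134 | 0.115 | 1.17 | 61% / 75% |
| 0.7 | 10% | 0.144 | 0.099 | 1.46 | 55% / 86% |
| 0.3 | 20% | 0.112 | 0.110 | 1.01 | 77% / 78% |
| 0.5 | 20% | 0.124 | 0.110 | 1.12 | 68% / 78% |
| 0.7 | 20% | 0.134 | 0.097 | 1.39 | 61% / 87% |

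For 0.5 SD, power without baseline PCS is 90-96% at e = 0 and 93-99% at e = 10-20%, so it stays above 85% throughout. One comparison shows what is lost. At r = 0.6 and e = 0, the two-visit model without baseline PCS has SE 0.149. A 6-month ANCOVA with baseline PCS has √(0.64 × 2/72) = 0.133. The second visit would then have bought nothing. With e = 20% the two are equal at r = 0.6.

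**Baseline as an outcome row.** Take a true effect of 0 at baseline and 0.5 SD at 6 and 12 months. With equal correlations each row has weight 1/3, so the constant-effect estimate has expectation (0 + 0.5 + 0.5)/3 = 0.33 SD. The straight-line interaction has slope 0.25 per visit about that mean, giving 0.08, 0.33 and 0.58 SD at baseline, 6 and 12 months. Nine assumed correlation sets, equal and unequal, were simulated with the SAP's p<0.05 switch. The interaction was significant in 71-99% of trials. The mean reported effect was 0.29-0.34 SD at 6 months and 0.48-0.61 SD at 12 months. A flat effect thus looks as if it grows.

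**After the change.** With outcomes at 6 and 12 months and baseline PCS as a covariate, the estimate is unbiased with the SEs in the fourth column. In the e = 0 case, a baseline row with arm means constrained equal at baseline was also checked and gave the same SEs and no bias.

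**The case against.** The strongest reply is that SAP 9.1 already adjusts all outcomes for the baseline score where that is appropriate. PCS has a baseline, and Protocol 12.3.2 sends continuous outcomes to the primary method. On that reading baseline PCS enters the model and nothing is lost. This is a fair reading and the text does not rule it out. It does not settle the matter, because the list in SAP 9.6 is specific and omits only this term; an analyst following that list would leave it out.

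A second reply is that the SAP nowhere says baseline is an outcome row. That stands. The heading names 6 and 12 months, and a constant effect over time is a natural starting assumption for two post-randomisation visits but not for a pre-treatment one. A reader might infer that the planned model distorts the arm effect, or would even show a waning effect as a growing one. The documents do not support that as a description of the plan. It needs a row the SAP does not state, together with time entered linearly.

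A third reply is that the power loss is overstated if sex, EHRA class, age and LVEF are assumed to explain nothing. That also stands, so the 10-20% rows should be used for 0.3 SD. Protocol 12.2 in any case accepts low power for smaller differences.

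**Conclusion.** The specification is incomplete and, taken literally, inefficient. On the favoured reading there is no bias with complete data. The standard error is 1-46% larger than it need be if the other covariates explain 10-20% of the variance, and 8-54% larger if they explain nothing. For 0.3 SD, power is about 55-77% against 72-87%. Every one of these figures depends on assumed correlations, and at r = 0.3 the loss is small. The understated 6-month effect (0.29-0.34 SD for a true flat 0.5 SD) applies only if an analyst makes baseline an outcome row.

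A reader might also infer that the main PCS result is at risk. It is not: the 6-month primary analysis and the separate 12-month PCS analysis both adjust for baseline PCS, and the sample size does not rest on this model. This is a free improvement to an additional secondary analysis, of minor to moderate importance.

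**What to change.** In the repeated-measures paragraph of SAP 9.6, state that the outcomes are PCS at 6 and 12 months and add baseline PCS to the covariates. An equivalent choice is to keep baseline as an outcome row, constrain the arm means to be equal at baseline, and treat visit as categorical.

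The cost is one sentence. Baseline PCS is already collected, no new data are needed, and the primary analysis does not change.
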